### 5.3 Measurements during the treatment cycle

All data collected during the administration of the therapy will be collected and reported in the appropriate data collection folder (CRF) by a co-investigator doctor from the team of [name].

#### 5.3.1 Safety assessment and appearance of adverse events:

An adverse event is considered any unfavorable and unwanted sign, symptom or disease found in a patient participating in a clinical study temporarily associated with the use of an experimental product, even if it does not necessarily have a causal relationship with the treatment received. Clinical and/or pathological conditions present prior to initiation of study treatment are considered adverse events only if they worsen after initiation of study treatment.

Every adverse event that occurred during the execution of the study will be recorded.

In the event of an adverse event, the Investigator will promptly institute the appropriate investigations and therapeutic measures. Any adverse event occurring during the study should be treated according to recognized treatment standards. If necessary, the patient will be withdrawn from the study.

The procedures foreseen by the study do not involve any additional risk for the patient's health.

The Investigator must promptly report, within 24 hours, any adverse event that occurs to patients during the study to the Ethics Committee, to the Promoter, in accordance with the provisions of the law.

In the event of accidents (defined by article 9, paragraph 1 of Legislative Decree 46/97 and by article 11, paragraph 1 of Legislative Decree 507/92) that may have occurred during the project, the reports will be sent to the Office V (Medical Device Supervision) of the DGDFSC (General Directorate of Medical Devices, Pharmaceutical Service and Care Safety) of the Ministry of Health, according to the procedures set out in Meddev 2.12-1 rev 6 year 2009, by the Promoter. The information relating to the accidents will also be sent to the Manufacturer.

### 5.3.2 Expected Adverse Events

Predicted adverse events include all those events that are expected to occur in association with any routine treatment. No serious adverse events have ever been reported in the literature regarding the use of tamsulosin.

Common effects (<1/10 cases, > 1 100 cases (1-10%)): dizziness, particularly on sitting or standing up. Abnormal ejaculation (ejaculation disorder). This symptom means that the seminal fluid does not leave the body through the urethra but enters the urinary bladder (retrograde ejaculation) or that the volume of seminal fluid is reduced or absent (ejaculation failure). Uncommon effects (>1/1000 cases, <1/100 cases (0.1-1%)): headache, palpitations (heart beats more frequently than normal and is also noticeable), decrease in blood pressure to example rising quickly from sitting or lying down often associated with dizziness, stuffy or runny nose (rhinitis), diarrhoea, nausea and vomiting, constipation, weakness (asthenia), rash, itching and hives.

Rare effects ((>1/10000 cases, <1/1000 cases (0.01-0.1%)): fainting and cases of sudden localized swelling of soft tissues of the body (e.g. of the throat and tongue), difficulty breathing and/or itching and rash (rash), as frequently in an allergic reaction (angioedema).

Very rare effects (<1/10,000 cases (<0.01%)): priapism (painful and prolonged involuntary erection requiring immediate medical treatment).

The most frequent adverse events from the use of tamsulosin were orthostatic hypotension, retrograde ejaculation and ejaculation failure, gastrointestinal disorders [31].

### 5.3.3 Adverse event reporting period

The adverse event baseline period for this study begins on day 0 and ends 30 days after study completion. All adverse events should be documented in the data collection record (CRF), as well as any other events considered potentially related to the device.

#### 5.4 Post-treatment evaluation protocol

All the variables will be collected by a co-investigator of [name] team during check-ups at pre-established intervals of 1, 3, 6 and 12 months (T1, T2, T3 and T4 respectively) and will be reported in the specific data collection folder (CRF).

- at 1 month (T1), 3 months (T2), 6 months (T3) and 12 months (T4):
- Personal data: identification number and initials of the patient's name and surname, date of birth, telephone number and e-mail address
- Medical history: IPSS, SF-36
- Physical examination: abdominal, urological including rectal examination
- Uroflowmetry: morphological analysis of the flow curve, Qmax, Volume of urine emptied, RPM).

#### 6. Sample size and statistical analysis of the data

A total of 250 patients will be recruited. The sample analysis was performed by the "GF Ingrassia" Department of Medical, Surgical Sciences and Advanced Technologies of the University of Catania. In particular, the design foresees a 1:1:1 randomization process in 3 arms. Expect a difference of at least 2 points in IPSS and Qmax and a standard deviation of 4, as described in previous studies (Morgia et al., 2014; Alcaraz et al., 2016), it is necessary to enroll 250 patients to obtain a power 90% statistic at a significance level of 0.05.

The statistical analysis of the data collected during the study, according to an intention-to-treat procedure, will be performed using statistical software such as IBM SPSS statistics version 23.0. The variables that will be collected in order to evaluate the efficacy of the therapy will be: chronological age, weight, BMI, smoking, diabetes, PSA, IPSS, Postvoiding Residual, Qmax, QMed, Voided volume, SF-36 score. A descriptive analysis of the patients included in the three arms will be performed using the appropriate frequency measures and indices of central tendency and dispersion. Considering one pair of the three arms at a time (1 vs. 2; 1 vs. 3; 2 vs. 3), the qualitative variables will be compared using the chi-squared test; the quantitative variables will be

compared using Student's t-test. The level of significance will be set at  $p < 0.05$ . For the variables that will be significant in the univariate analysis, multivariate analyzes will be performed using appropriate regression models to control for the effect of the covariates.

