### 2.1 Primary Outcomes:

1) Evaluate the efficacy of the treatment in terms of subjective improvement of urinary symptoms by performing IPPS and SF-36 questionnaires and evaluate the objective improvement of urinary symptoms by performing uroflowmetry before and during treatment (during control visits follow-up at 1,3,6 and 12 months) by evaluation of the ultrasound post-voiding residue, comparing patients receiving combined therapy with tamsulosin+peaprostil (Arm 1) with patients receiving monotherapy with tamsulosin (Arm 3).

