## 5.2 Pre-treatment assessment

All patients will undergo an accurate analysis of the following parameters (T0).

- Personal data: identification number and initials of the patient's name and surname, date of birth, telephone number and e-mail address.
- General characteristics: gender, weight, height, smoker, coffee and/or tea intake, allergies, job, sport, diabetes mellitus.
- Medical therapy in progress.
- Remote pathological history: previous surgical interventions, underlying pathologies and number of deliveries.
- Past pathological history and diagnosis: starting date and type of symptomatology
- Assessment of quality of life (QoL questionnaire).
- Voiding assessment (IPSS questionnaire)
- Physical examination: abdominal, urological including rectal examination.
- Uroflowmetry (morphology of the curve, Qmax, Vol, RPM-residual evaluation post urination)

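### Section 6 plans an unadjusted t-test although baseline IPSS and Qmax are collected, and its 250 for 90% power holds only with complete data on one endpoint in one arm pair

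*Combined protocol and SAP*

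**What the plan says.** Section 6 sets the sample size: "Expect a difference of at least 2 points in IPSS and Qmax and a standard deviation of 4", from which it concludes that "it is necessary to enroll 250 patients to obtain a power 90% statistic at a significance level of 0.05". Allocation is 1:1:1 across three arms. The figure is given for IPSS and Qmax together. No visit and no arm pair is attached to it.

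Section 2.1 does name a primary comparison, "comparing patients receiving combined therapy with tamsulosin+peaprostil (Arm 1) with patients receiving monotherapy with tamsulosin (Arm 3", but across several measures and with assessments "during control visits follow-up at 1,3,6 and 12 months". No section singles out one primary endpoint or one primary visit.

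For the analysis, Section 6 says quantitative variables will be "compared using Student's t-test", one arm pair at a time. Adjustment comes only afterwards and only on a condition: "For the variables that will be significant in the univariate analysis, multivariate analyzes will be performed using appropriate regression models".

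Section 5.2 lists the T0 measurements. They include "Voiding assessment (IPSS questionnaire" and, under uroflowmetry, Qmax. Section 5.3.1 foresees that patients may leave: "If necessary, the patient will be withdrawn from the study". Section 6 names intention-to-treat, but no section gives an expected loss, an inflation of the sample size or a rule for missing outcomes.

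**The concern.** Two features of Section 6 work against each other. The sample size is used up in reaching 90% with every outcome observed, yet it is presented as the number to enrol in a trial with 12 months of follow-up. The analysis also leaves unused the one resource that could offset some loss at no cost, the T0 value of the same variable. The conditional regression does not help, because it runs only where the unadjusted test has already succeeded and so cannot rescue a comparison which that test misses.

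At stake is the chance of missing a true 2-point difference. It is about 11% with complete data and about 14 to 16% at an assumed 10 to 15% loss. A second consequence is that the 90% cannot be matched to any particular result until one endpoint and one visit are named.

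**Working it through.** **Inputs.** From Section 6: difference 2, SD 4, significance level 0.05, power 90%, total 250, three equal arms, so 250/3 = 83.3 per arm. From Section 4.2: IPSS at entry between 8 and 14. Assumed: a two-sided test (Section 6 does not say; a one-sided calculation would give 207, not 250), loss rates of 5 to 20%, baseline correlations r of 0.2 to 0.5, and a baseline IPSS SD of 2 to 3.

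**1. The plan's own figure.** Normal approximation: n per arm = 2 × (1.96 + 1.2816)² × (4/2)² = 84.06, so 85 per arm or 255 in total. The exact t-test (noncentral t, standardised difference 2/4 = 0.5) needs 86 per arm for 90%. At 83 per arm it gives 89.3%. The stated 250 for 90% therefore reproduces to rounding, for one endpoint and one arm pair with complete data.

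**2. Missing outcomes, unadjusted t-test.** Per-arm n = 83.3 × (1 − loss).

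| Assumed loss | Per arm | Power |
|---|---|---|
| 0% | 83 | 89.3% |
| 5% | 79 | 87.8% |
| 10% | 75 | 86.0% |
| 15% | 71 | 84.1% |
| 20% | 66 | 81.4% |

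(At 20% the exact 66.7 per arm was rounded down; unrounded it gives 81.7%.) The drop at 10 to 15% loss is 89.3 − 86.0 = 3.3 to 89.3 − 84.1 = 5.2 points.

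**3. ANCOVA on the T0 value, 10% loss (75 per arm), one degree of freedom fewer.** Section 6 does not say whether the SD of 4 belongs to the follow-up value or to the change from baseline, so both are shown.

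*SD 4 is the follow-up SD.* Residual SD = 4 × √(1 − r²).

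| r | Residual SD | Power |
|---|---|---|
| 0.2 | 3.919 | 87.4% |
| 0.3 | 3.816 | 89.0% |
| 0.5 | 3.464 | 94.0% |

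At 15% loss (71 per arm) the same cases give 85.5, 87.3 and 92.7%, against 84.1% for the t-test.

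*SD 4 is the SD of change, for IPSS.* A score confined to 8 to 14 has an SD of at most (14 − 8)/2 = 3, hence a baseline SD b of 2 to 3. The follow-up SD f solves 16 = b² + f² − 2rbf, and the residual SD is f × √(1 − r²). For b = 2 and r = 0.5: f = 1 + √13 = 4.606, so the residual SD is 4.606 × 0.866 = 3.989.

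| r | Residual SD, b = 2 | Power | Residual SD, b = 3 | Power |
|---|---|---|---|---|
| 0.2 | 3.809 | 89.2% | 3.246 | 96.3% |
| 0.3 | 3.926 | 87.3% | 3.524 | 93.2% |
| 0.5 | 3.989 | 86.2% | 3.933 | 87.2% |

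The comparator throughout is 86.0%, the t-test on whichever quantity has the SD of 4. The smallest gain is 86.2 − 86.0 = 0.2 points.

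**4. The alternative of more patients.** Holding 90% with the unadjusted t-test: 86/0.90 = 95.6, so 96 per arm (288) at 10% loss; 86/0.85 = 101.2, so 102 per arm (306) at 15%.

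**The case against.** The strongest reply is that little is wrong here. The arithmetic is sound, an unadjusted t-test is valid in a randomised trial, and the loss rate comes from the review and not from the protocol. Section 5.3.1 allows withdrawal but gives no frequency and does not say that outcome collection stops. Power stays above 81% even at 20% loss. With one difference, one SD and equal allocation, the power is the same for any arm pair, so linking it to Arm 1 versus Arm 3 is a cross-reference and changes no number. All of this stands. It is why the point is an improvement and a clarification, and why 250 is kept.

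Several stronger readings are tempting, and the documents do not support them:

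- *That 250 is miscalculated.* It reproduces to rounding.
- *That the trial is underpowered.* This would need a loss rate the documents do not give, and no rate examined takes power below 80%.
- *That the pairing of IPSS with Qmax lowers the power to about 80%.* If both had to succeed and were independent, power would be about 0.893² = 0.797. Nothing says both must succeed.
- *That ANCOVA would bring power to 94 to 98%.* Taking SD 4 as the SD of change with equal variances at baseline and follow-up gives 98, 97 and 94% at r = 0.2, 0.3 and 0.5. But that needs a baseline SD of 4/√(2(1 − r)) = 3.16, 3.38 and 4.00, all above the IPSS ceiling of 3. Those figures should not be quoted for IPSS.

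It is also fair to say that ANCOVA among patients with an observed outcome does not settle how missing outcomes are treated under intention-to-treat. That rule needs its own sentence in Section 6.

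**Conclusion.** The point holds as a modest one that should be fixed. Directly from the text: the primary comparison ignores baseline values that are already collected, adjustment depends on prior significance, 250 is the enrolment figure with no reserve, and the power is tied to no single endpoint or visit. By calculation: 89.3% with complete data, and about 84 to 86% at 10 to 15% loss. The size of that drop rests on the assumed loss.

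Baseline adjustment at 10% loss gives 87, 89 and 94% (r = 0.2, 0.3, 0.5) if SD 4 is the follow-up SD. For IPSS it gives 89–96, 87–93 and 86–87% if SD 4 is the SD of change. These rest on assumed correlations and baseline SDs. The gain can be negligible, and in no case shown was there a loss.

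**What to change.** Keep 250 and change two things in Section 6.

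1. Make the primary Arm 1 versus Arm 3 analysis an ANCOVA of the follow-up value on arm and the T0 value of the same variable, fitted whether or not any univariate test is significant.

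2. Replace the power sentence with one that is explicitly conservative, for example:

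> 250 randomised (about 83 per arm) gives about 89% power at two-sided 0.05 with complete data, and about 84–86% if an assumed 10–15% lack the outcome, for a difference of 2 (SD 4) on [one named endpoint] at [one named visit], Arm 1 versus Arm 3, before baseline adjustment; the planned ANCOVA is expected to have at least this power.

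The words on baseline adjustment matter: without them the protocol would quote t-test power for a test it no longer uses. The endpoint and visit are the sponsor's choice, to be fixed before the 3- and 6-month analyses planned in Section 7. The sponsor should also state whether the SD of 4 is the follow-up SD or the SD of change.

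Cost: one paragraph, a changed primary model and a slightly less favourable stated power. No extra patients, visits or measurements are needed. Holding 90% with the unadjusted test would instead need 288 or 306 patients at an assumed 10 or 15% loss.

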Controlled studies show that  $\alpha 1$ -blockers typically reduce IPSS by approximately 30-40% and increase Qmax by approximately 20-25% [17].  $\alpha 1$ -blockers do not reduce prostate size [18]. The most frequent adverse events of  $\alpha 1$ -blockers are asthenia, dizziness and orthostatic hypotension. They do not negatively affect libido, have a small beneficial effect on erectile function, but sometimes cause abnormal ejaculation [19]. Originally, abnormal ejaculation was associated with retrograde ejaculation, but more recent data show that it is due to a decrease or absence of seminal fluid during ejaculation.

Thus,  $\alpha 1$ -blockers are often considered the first-line pharmacological treatment of LUTS due to their rapid action, good efficacy, low frequency and severity of adverse events. However,  $\alpha 1$ -blockers do not prevent the onset of acute urinary retention and the need for surgery for BPH.

Another category of drugs involved in the treatment of BPH are the 5 alpha reductase inhibitors (5-ARIs). The effects of androgens on the prostate are mediated by dihydrotestosterone (DHT), which is converted from testosterone by the enzyme 5 $\alpha$ -reductase. There are two isoforms of this enzyme:

- 5 $\alpha$ -reductase type 1, activity predominant in extraprostatic tissues, such as skin and liver.

- 5 $\alpha$ -reductase type 2, predominant in the prostate.

Two 5-ARIs are available for clinical use: dutasteride and finasteride. Finasteride inhibits type 2 5 $\alpha$ -reductase only, whereas dutasteride inhibits type 1 and type 2 5 $\alpha$ -reductase with similar potency. 5 $\alpha$ -reductase inhibitors work by inducing apoptosis of prostate epithelial cells [20] leading to a reduction in prostate size by approximately 18-28% and a decrease in circulating PSA levels by approximately 50% after six to twelve months of treatment [21].

Placebo-related clinical effects are observed after a minimum treatment duration of at least six to twelve months. An indirect comparison and a direct comparative trial (twelve months duration) indicate that dutasteride and finasteride are equally effective in the treatment of LUTS [21, 23]. The greater the baseline prostate volume, the greater the symptomatic benefit of dutasteride over tamsulosin.

5 $\alpha$ -reductase inhibitors, but not  $\alpha$ 1-blockers, reduce the long-term risk (> 1 year) of acute urinary retention or the need for surgery [22, 24].

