#### 4.2 Inclusion criteria

- o Male patients aged 40 years or older
- o Patients with baseline IPSS questionnaire between 8 and 14
- o Patients with prostate volume  $\leq$  60 cc assessed by transrectal ultrasound (TRUS)
- o Patients who have a Qmax  $\leq$  15 ml/sec on uroflowmetry
- o Patients who show a post-voiding residue  $\leq$  120 ml on extemporaneous ultrasound
- o Patients who have signed the informed consent for participation in the study
- o Patients able to understand the conditions of the study and to participate for the full duration.

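### Section 6 names intention-to-treat but pairs it with visit-wise t-tests and no analysis set, missing-value rule or plan for outcomes after withdrawal, so it reads most naturally as an available-case comparison

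*Combined protocol and SAP*

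**What the plan says.** Section 6 states the principle once: "The statistical analysis of the data collected during the study, according to an intention-to-treat procedure". It then lists descriptive statistics, pairwise chi-squared tests for qualitative variables, and, for quantitative variables, that they will be "compared using Student's t-test", again one pair of arms at a time. Regression is a conditional second step: "For the variables that will be significant in the univariate analysis, multivariate analyzes will be performed using appropriate regression models". No section defines who is in the intention-to-treat set, how a missing value is treated, or a sensitivity analysis for missing data.

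Section 5.3.1 provides that "If necessary, the patient will be withdrawn from the study", and does not say whether outcomes are still measured afterwards. Section 5.4 schedules all variables at T1 to T4 (1, 3, 6 and 12 months) and does not make this depend on the patient still taking study product.

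The primary outcomes in Section 2.1 (IPSS, SF-36, uroflowmetry, post-void residue) are essentially quantitative, so the t-test is the test that governs them. Section 2.1 also speaks of "performing uroflowmetry before and during treatment (during control visits follow-up at 1,3,6 and 12 months", which leaves room for a change-from-baseline reading. The sample-size paragraph rests on this statement: "Expect a difference of at least 2 points in IPSS and Qmax and a standard deviation of 4". It has no allowance for loss.

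**The concern.** A t-test at a visit needs a value at that visit. A t-test on change scores needs one too, so the change-score reading does not help a patient who has left. The regression step has no missing-data rule either, and it is reached only after a significant univariate result. With nothing else written, the intention-to-treat label has no operational content, and the comparison becomes one of the patients who happen to have been measured.

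Two things are at stake. If loss is related to outcome and differs between arms, the estimated difference shifts, in either direction. And whatever the loss rate, the decisions on who counts and how gaps are filled remain open until data are in hand. Section 7 makes this more pressing, since it schedules preliminary analyses of the 3- and 6-month data.

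**Working it through.** **1. The plan's own figure.** Inputs from Section 6: difference 2, SD 4, power 90%, significance level 0.05 (taken as two-sided), 250 patients in three equal arms.

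n per arm = 2 × (1.960 + 1.282)² × 4² / 2² = 84.1, or 85 after rounding up with the t correction; 3 × 85 = 255. The stated 250 is 5/255, or 2%, lower. It is reproduced for one unadjusted pairwise comparison in which every randomised patient supplies a value. A one-sided test would need 69 per arm (207 in total) and does not reproduce it.

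**2. Power if only available cases are used.** Loss rates are assumptions, since the plan gives none. Noncentral t, standardised difference 2/4 = 0.5:

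| Loss, equal in both arms | n per arm | Power per pair |
|---|---|---|
| 0% | 83 | 0.893 |
| 10% | 75 | 0.860 |
| 20% | 66 | 0.814 |

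**3. Bias formula.** Let d be the proportion lost in an arm and g the mean IPSS of leavers minus that of stayers. The full-arm mean is the stayer mean plus d × g, so the available-case Arm 3 minus Arm 1 difference falls short of the full one by

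shortfall = d3 × g3 − d1 × g1.

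- Equal d and equal g: 0.
- d1 = 0.10, d3 = 0.20, common g = 4: 0.8 − 0.4 = 0.4 points.
- d1 = 0.10, d3 = 0.25, common g = 4: 1.0 − 0.4 = 0.6 points.
- Equal 20% loss with g1 = 0 and g3 = 4: 0.8 points.
- Corner values for d in 0–0.25 and g in 0–4: 0.25 × 4 − 0 = +1.0, or −1.0 with the arms exchanged.

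**4. Simulation.** From the plan: follow-up SD 4, true 12-month difference 2, 83 per arm, and the entry criterion "Patients with baseline IPSS questionnaire between 8 and 14". Assumed: T0 uniform on the integers 8 to 14 (SD 2.0), slope of follow-up on T0 0.5, correlation 0.5 between follow-up visits, Arm 1 effects of 1, 1.5, 2 and 2 points at T1–T4, and dropout before T2, T3 or T4 with log-odds depending on the previous IPSS. The slope-0.3 rows used 4,000 runs (Monte Carlo standard error 0.01). A slope of 0.3 per point is an odds ratio of exp(0.3 × 4) = 3.3 per SD, which is strong; 0.1 gives exp(0.1 × 4) = 1.5.

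| Loss Arm 1 / Arm 3 | Slope | t-test | Change-score t-test | Repeated-measures model |
|---|---|---|---|---|
| 10% / 10% | 0.3 | 1.99 | – | 1.98 |
| 20% / 20% | 0.3 | 2.00 | – | 2.00 |
| 10% / 15% | 0.3 | 1.88 | 1.90 | 1.99 |
| 10% / 20% | 0.3 | 1.78 | 1.84 | 2.00 |
| 10% / 25% | 0.3 | 1.65 | 1.74 | 1.98 |
| 20% / 10% | 0.3 | 2.21 | – | 2.00 |
| 25% / 10% | 0.3 | 2.34 | – | 2.02 |
| 10% / 20% | 0.1 | 1.92 | – | about 2.0 |
| 10% / 25% | 0.1 | 1.87 | – | about 2.0 |

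At a slope of 0.05 the t-test gives 1.96 and 1.93 for the last two loss patterns. The formula in step 3 agrees with the simulation: the realised gap at slope 0.3 was about 2.2 to 2.3, and (0.20 − 0.10) × 2.25 = 0.22, matching 2 − 1.78.

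**5. Limit of the model.** If dropout depends on the unseen current value (slope 0.3), the model gives 1.86 and 1.75 at 10%/20% and 10%/25% loss, against 1.73 and 1.54 for the t-test. It reduces this bias but does not remove it.

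**The case against.** The strongest reply is that the plan is silent rather than wrong. A t-test can be run on imputed values, and naming intention-to-treat may have been meant that way. This stands to the extent that a reader might infer a stated completers-only rule, and there is none. The available-case comparison is the natural reading of the text, not a written decision.

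A reader might also infer that Section 6 offers nothing but t-tests, or that outcomes stop when product stops. Neither is supported. Chi-squared tests and conditional regression are named as well, and Section 5.4 schedules T1–T4 without requiring the patient to be on product. Only withdrawal from the study itself is left unaddressed, and consent wording, which might bear on it, is not available to this review.

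The most tempting inference is that the Arm 1 against Arm 3 result will be biased. The documents do not support it. They give no loss rate; both arms take tamsulosin; the introduction credits alpha-blockers with "low frequency and severity of adverse events" and describes side effects of herbal products as usually mild. With equal loss and equal gaps the t-test is unbiased. The larger shifts come from a strong dropout slope, and the ±1-point range needs corner values. What remains is that unequal loss cannot be excluded: the plan describes neither placebo nor blinding, and in the 1 vs 2 and 2 vs 3 comparisons one arm takes tamsulosin and the other does not.

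Finally, a mixed model rather than imputation is partly a preference. That is fair, but the four visits are already collected and the model uses them directly.

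**Conclusion.** The concern holds in this limited form: intention-to-treat is named without an analysis set, a missing-value rule or a statement on outcomes after withdrawal, and the stated t-test naturally becomes an available-case comparison. The omission is certain; its numerical effect is not.

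Under the assumed loss of 10% in Arm 1 and 20% to 25% in Arm 3, the 2-point difference is understated by about 0.1 at a slope of 0.1 and by 0.2 to 0.35 at a slope of 0.3. It is overstated if Arm 1 loses more, and unaffected under equal loss and equal gaps. Power per pair falls from about 89% to 86% or 81% at 10% or 20% loss. No material power gain is claimed for the model. Nor does this show the sample size to be miscalculated: 250 reproduces on its own inputs and simply carries no margin for loss. The change should be made, but the hypothetical sizes are not a reason to rank it higher.

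**What to change.** **(a) Section 5.3.1.** Leave every decision on stopping treatment or withdrawal as it is. Add that a patient who stops study product, or is withdrawn after an adverse event, continues the scheduled T1–T4 outcome assessments unless he withdraws consent to follow-up or the investigator considers it not possible, with date and reason recorded.

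**(b) Section 6.** Replace the between-arm t-tests for IPSS, Qmax, SF-36 and post-void residue with a mixed model for repeated measures on T1–T4: arm, visit, arm × visit, T0 value and T0 × visit, with unstructured covariance. Omit the T0 terms where no T0 value was collected; Section 5.2 lists a quality-of-life questionnaire at T0 without naming SF-36. Run the model whatever the univariate result, with patients in their assigned arm. Report each difference with its 95% confidence interval, and name one visit as primary before data are seen. Patients with no T1–T4 value are counted by arm and enter (c).

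**(c) One sensitivity analysis.** Multiple imputation of all randomised patients, with imputed values made worse by 0, 0.25, 0.5, 0.75 and 1 SD of the outcome concerned (1 SD is 4 points for IPSS on Section 6's figure). Apply the shift to each arm in turn, so that all three pairwise comparisons are covered. This is needed because the model in (b) does not remove bias from dropout that depends on unseen values.

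**Cost.** New wording in two sections, a little more analysis work, and already scheduled visits for some patients off product. SPSS, the software named in Section 6, fits the model.

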### 2.2 Secondary Outcomes:

1). Evaluate the tolerability profile of the study therapy, analyzing the side effects.  
2). Evaluate the efficacy of the treatment in terms of subjective improvement of urinary symptoms by performing IPPS and SF-36 questionnaires and evaluate the objective improvement of urinary symptoms by performing uroflowmetry before and during treatment (during follow-up visits -up at 1,3,6 and 12 months) by means of ultrasound evaluation of the post-voiding residue, comparing the patients of the 3 study groups (Arm 1, 2 and 3).

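### Section 6 places age, weight, BMI, smoking and diabetes among the efficacy variables and, as written, tests them between randomised arms, with about a 43–48% chance of at least one spurious significant difference

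*Combined protocol and SAP*

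**What the plan says.** Section 6 gives a single list of the variables that are to show efficacy: "chronological age, weight, BMI, smoking, diabetes, PSA, IPSS, Postvoiding Residual, Qmax, QMed, Voided volume, SF-36 score". That makes twelve variables.

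One sentence plans a descriptive analysis of the three arms. The next takes the arms two at a time (1 vs 2, 1 vs 3, 2 vs 3). It states that "the qualitative variables will be compared using the chi-squared test" and assigns Student's t-test to the quantitative ones, at p<0.05. The section then says: "For the variables that will be significant in the univariate analysis, multivariate analyzes will be performed using appropriate regression models", with the aim of controlling for covariates. It does not name the covariates.

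Section 5.2 collects the characteristics at T0: "General characteristics: gender, weight, height, smoker, coffee and/or tea intake, allergies, job, sport, diabetes mellitus". The follow-up list in Section 5.4 does not repeat weight, smoking or diabetes.

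Section 2.2 makes tolerability the first secondary outcome: "Evaluate the tolerability profile of the study therapy, analyzing the side effects". Section 6 names no summary or comparison for side effects.

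**The concern.** Weight, smoking and diabetes are scheduled only before treatment, and age cannot respond to it. A between-arm difference in these variables cannot be evidence of efficacy. If randomisation was properly carried out, the null hypothesis of such a test is true by design, and any significant result is a chance finding.

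Two things are at stake. First, a report that follows Section 6 literally could show significant differences among its efficacy variables that carry no information about PEAPROSTIL 600. Second, if significance in the univariate step decides what enters the regression, chance imbalance rather than prognostic value would select the covariates.

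**Working it through.** **The plan's own figure.** Section 6 gives a difference of 2, SD 4, power 90%, alpha 0.05 and N = 250 in three equal arms. Two-sided, n per arm = 2 × [4 × (1.960 + 1.2816) / 2]² = 84.06. Three arms need 252.2, or 3 × 85 = 255 after rounding up. The stated 250 is reproduced to within 3%. With 83 per arm, power by the noncentral t distribution is 89.3%. The sample size is therefore sound on its own terms and this point does not affect it.

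**Number of baseline tests.** 5 characteristics × 3 pairs = 15 tests. Expected false positives: 15 × 0.05 = 0.75.

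**Chance of at least one false positive.**
- Treating all 15 tests as independent gives 1 − 0.95¹⁵ = 53.7%. This is too high, because the three pairwise tests of one variable share arms.
- Allowing for shared arms, one variable has about a 12.2% chance of a significant result in some pair. For five independent variables, 1 − 0.878⁵ = 47.8%.
- Simulation with 83/83/84 men and no true differences gives about 48% with weight and BMI uncorrelated, and about 43–45% with a correlation of 0.8 to 0.9.
- For Arm 1 vs Arm 3 alone, 1 − 0.95⁵ = 22.6% under independence. Simulation gives 21–23%.

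The simulations assume 25% smokers, 15% with diabetes and independence apart from weight and BMI. None of these inputs is in the documents.

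**If baseline p-values choose the covariate.** Take 83 per arm, difference 2, SD 4, and one covariate with correlation r to the outcome. Fixed adjustment reduces the SD to 4 × √(1 − r²).
- r = 0.2: SD = 3.92, SE = 3.92 × √(2/83) = 0.608, and 2/0.608 = 3.29. Power is about 90%.
- r = 0.5: SD = 3.46, SE = 0.538, and 2/0.538 = 3.72. Power is about 96%.

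| Strategy | r = 0.2 | r = 0.5 |
|---|---|---|
| Adjust only if the baseline test is significant (simulated) | about 90% | about 90–91% |
| Adjustment fixed in advance | about 90% | about 96% |

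The p-value rule is slightly conservative: its type I error at r = 0.5 is about 4.4%.

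**Side effects.** Section 5.3.2 puts most listed tamsulosin effects at 1% or below, so fewer than 83 × 0.01 = 0.83 men per arm would be expected with each. Even 10% in one arm against none in the other gives an expected count of 83 × 0.10 / 2, or about 4 per arm, which is small for a chi-squared test.

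**The case against.** The strongest reply is that the efficacy label is loose wording or translation and that the five characteristics were meant as covariates. That is possible. It does not remove the problem, because a separate sentence already provides the descriptive analysis and the testing sentence exempts nothing.

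Several stronger readings that a reader might infer are not supported:

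- *That the chi-squared test can apply only to smoking and diabetes.* They are the only naturally qualitative items in the list. But flow-curve morphology is recorded at each visit and adverse events go into the CRF, and the testing sentence does not refer back to the list explicitly.
- *That the plan would probably produce a spurious finding.* For the five characteristics the chance is below one half. A figure of about 77% arises only if all twelve variables are also tested at T0, which Section 6 does not state.
- *That chance imbalance certainly selects the covariates.* The regression sentence can equally mean that outcomes found significant are then modelled with adjustment. The selection harm belongs to one reading only.
- *That the primary comparison is invalid.* Baseline testing does not inflate type I error for IPSS or Qmax.
- *That testing characteristics leaves side effects without a test.* The tolerability gap is a separate omission, and side effects would not be expected in a list of efficacy variables.

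The objection to the power figures also stands in part. The gain to 96% needs r = 0.5, which the documents do not support for these characteristics; at 0.2 the gain is negligible.

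**Conclusion.** The concern holds in a limited form. As written, Section 6 tests patient characteristics between randomised arms as part of the efficacy analysis. This is an inappropriate rule, not merely a missing detail. The chance of at least one spurious significant result is about 43–48% over three pairs and 21–23% for Arm 1 vs Arm 3, under the stated prevalence and correlation assumptions.

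The consequence is a potentially misleading report and, on one reading of the regression sentence, covariates chosen by chance. The loss of power from that ranges from almost nothing to about 5 points, depending on an assumed correlation. The sample size and the validity of the IPSS and Qmax comparisons are not undermined. The change is worth making because the defect is clear and the remedy simple.

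**What to change.** Split the list in Section 6.

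1. **Baseline characteristics** (age, weight, BMI, smoking, diabetes and T0 values of the outcomes): summarise by arm with counts, means and SDs, without significance tests.
2. **Covariates:** name them in advance, for example the T0 value of the outcome being analysed, and state that baseline p-values play no part in choosing them.
3. **Outcomes:** apply between-arm tests only to post-baseline outcomes. State for PSA and QMed when they are measured and which group they belong to, since neither Section 5.2 nor Section 5.4 names them.

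As a separate, minor point, add a sentence on tolerability: summarise side effects by arm and compare the proportion of men with at least one, using Fisher's exact test where counts are small. Avoid a chi-squared test on each rare effect.

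The cost is a few sentences in Section 6. Nothing changes in sample size, visits or procedures.
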